#### 2.5 Treatment Regimens

Either sofpironium bromide gel, 15% or vehicle gel (placebo) topically applied to the axillae once daily at bedtime for 42 consecutive days.

#### 2.6 Sample Size Determination

Sample size estimation was performed for the co-primary efficacy endpoints based on the results of a Phase 2b study (BBI-4000-CL-203):

- HDSM-Ax-7 responder analysis: 2-point improvement response rates of 29.8% and 53.7% were assumed for the vehicle and sofpironium bromide gel, 15% arms, respectively. The power is 0.95 with 116 subject per arm and a total of 232 subjects.
- GSP: using rank-transformed GSP data for change from baseline to EOT, a difference of 16.6 in mean ranks between vehicle and sofpironium bromide gel, 15% arms, with a pooled standard deviation of approximately 39.5, was used for this purpose. Normal approximation yielded a sample size estimate of 296 subjects for the study, 148 in each arm, in order to achieve 0.95 power for the GSP co-primary endpoint.

A chi-square test for the HDSM-Ax-7 endpoint and a two-sample t-test for the GSP endpoint were used to estimate the above sample size and power for each endpoint. With approximately 300 evaluable subjects, the overall study power to demonstrate a statistically significant treatment effect (two-sided p < 0.05) for both co-primary

endpoints simultaneously is greater than 0.90 (with greater than 0.95 power for each of HDSM-Ax-7 and GSP). It is estimated that 350 total subjects will need to be randomized (in a 1:1 allocation) for there to be 300 subjects completing the co-primary efficacy assessments (approximately 15% drop-out rate).

Additionally, sample size estimation was also performed using non-rank-transformed GSP data. An expected mean treatment difference of 73 mg with a pooled standard deviation of approximately 170 was used for this purpose. This yielded a reduced sample size estimate compared with the target of 300 subjects completing the co-primary efficacy assessments in order to achieve 0.95 power for GSP, further indicating that our sample size estimations are conservative.

#### 3. GENERAL ANALYSIS AND REPORTING CONVENTIONS

#### 3.1 Reporting Conventions

The following is a list of general analysis and reporting conventions to be applied to this study, unless otherwise specified.

All data displays (tables, listings, and figures) will have a header showing the sponsor company name, protocol number, page number, and display status (i.e. "DRAFT" or "FINAL"), as well as a footer indicating file name and run date/time. Summary tables and data listings will be summarized by treatment, as appropriate. All data collected perprotocol will be listed. Derived variables may also be listed.

Categorical variables will be summarized using counts (n) and percentages (%) and will be presented in the form "n (xx.x)." If a count is 0, no percentage will be shown. If a percentage is 100%, 100% will be shown with no decimal place. To ensure completeness, summaries for categorical variables will include all categories, even if no subjects had a response in a particular category. Unless otherwise specified, the denominator for each percentage will be based on the number of subjects with available data in the population being summarized. If there are missing values, counts will be shown but will not be included in percentage calculations.

Continuous variables will be summarized using mean, standard deviation (SD), minimum, maximum, median, and number of subjects. The mean and median will be reported to an additional level of precision than the original observation in its rawest form (i.e. on the eCRF), and the SD and other measures of variability (e.g. standard error) will be reported to two additional levels of precision than the original observations. The minimum and maximum will be the same precision as the original data. In general, any calculated values, such as those due to unit conversion, will be rounded to the same number of decimal places as the original data.

Unless otherwise specified, all statistical tests will be 2-sided using  $\alpha$ =0.05. Estimates and confidence intervals will be reported to 1 more decimal than the original data. P-values will be reported to 4 decimal places. P-values less than 0.0001 will be displayed as "<0.0001"; p-values greater than 0.9999 will be displayed as ">0.99999".

Summary tables and data listings:

- No preliminary rounding will be performed; rounding will only occur after analysis.
- Data from subjects excluded from an analysis population will be presented in the data listings but will not be included in the calculation of summary statistics, where applicable.

- Data from each subject will be separated by a blank line. Within a data listing, if a descriptive item appears line after line (e.g., repetition of a subject number, date, visit, etc.), only the first occurrence will be displayed (e.g., in Listing of Vital Signs, subject number, date and visit will only be displayed on first row when presenting all parameters collected at same visit). Repetition of actual results or outcomes (e.g., Adverse Events (AEs), lab results, vital sign values, etc.) will not be collapsed.
- Data listings will be sorted by site, subject, treatment, and week and/or time of assessment, unless otherwise noted.
- When change from baseline is calculated, baseline is the last observation obtained prior to dosing of the study drug unless otherwise specified.

Mock tables and data listings will be provided as attachments to this analysis plan. Minor changes to the mocks after formal SAP approval will not necessitate re-approval unless changes to the text of the SAP are required.

All statistical deliverables will be produced, validated, and reviewed for accuracy/consistency in accordance with Rho, Inc. standard operating procedures and the processes described in the statistical validation plan.

SAS® (SAS Institute, Cary, North Carolina) statistical software, version 9.4 or later, will be used for all analyses. Adverse Events and Medical History will be coded using the most recent version of the Medical Dictionary for Regulatory Activities (MedDRA). Concomitant medications will be coded using the latest version of the World Health Organization (WHO) Drug and Anatomical-Therapeutic-Chemical (ATC) classification and preferred term.

#### 3.2 Standard Calculations

Unless otherwise noted, baseline is defined as the last observed data value prior to the receiving of the first application of treatment for treated subjects, and the last observed data value prior to the randomization date for randomized subjects who were not treated. The baseline derivation can include unscheduled visits.

Study day will be determined as:

- The assessment/event date minus the date of first dose of gel, if the assessment/event date is prior to the date of first dose of gel; and
- The assessment/event date minus the date of first dose of gel + 1, if the assessment/event date is on or after the date of first dose of gel. For example, Day 1 is defined as the date of the first dose of gel.

Note that if the subject is randomized but not treated then the randomization date will be Day 1 for Schedule of Event purposes. Change from baseline will be calculated as the post-baseline data value minus the baseline value. Percent change from baseline will be calculated as the change from baseline divided by the baseline value, multiplied by 100.

Unless otherwise noted, values reported as greater than or less than some quantifiable limit (e.g., "< 2.0") will be summarized as such in summary tables and figures. However, analysis will be performed using the numeric equivalent, e.g. "<2.0" will be analyzed as 2.0. Summary tables and figures will be footnoted when such practices occur.

Partial or missing dates used in calculations of duration may be imputed with logic similar to that of Adverse Events (Section 9.2).

#### 3.3 Duplicate Subjects

During the course of the BBI-4000-CL-302 study, some subjects were identified as having registered for study participation at more than one site and/or in the first Phase 3 pivotal study (BBI-4000-CL-301); these subjects are said to be duplicate subjects. Duplicate subjects are identified as such in the individual study subject listings.

For analyses using the Intent-to-treat (ITT) Population or the Safety Population: (a) duplicate subjects with repeat registrations in the same study will have each registration analyzed as a different study subject with his/her unique subject ID; (b) For subjects who registered to both BBI-4000-CL-301 and BBI-4000-CL-302, the registrations will remain in each study as subjects for the respective study.

Duplicate subjects will be removed from the modified ITT (mITT) Population (See Section 4) for the co-primary efficacy endpoints, secondary efficacy endpoints and sensitivity analyses of the co-primary efficacy endpoints.

#### 4. ANALYSIS POPULATIONS

Identification of the subjects to be included in each analysis population will be determined and finalized prior to database lock and unblinding. Subjects will be classified into the Safety, Intent-to-Treat (ITT), Per-Protocol (PP), and modified Intent-to-Treat (mITT) populations according to the following definitions:

#### Safety Population

The Safety Population will include all subjects randomized in the study who received study drug, either vehicle or sofpironium bromide, 15%, at least once. Subjects will be analyzed according to the treatment actually received. If a subject receives any sofpironium bromide gel, 15%, the subject will be analyzed in the sofpironium bromide gel group. Otherwise the subject will be included in the vehicle group.

#### Intent-to-Treat (ITT) Population

The ITT Population will include all subjects who were randomized. Subjects will be analyzed according to the treatment group to which they were randomized, regardless of post-randomization protocol deviations, including no treatment or wrong treatment received.

#### **Per-Protocol (PP) Population**

The PP Population will be a subset of the mITT Population and will include subjects who meet the following criteria:

- Meets all inclusion/exclusion criteria
- Has not taken or applied any interfering concomitant medications
- Completed the following visits:
  - Visit 2 GSP 1, and the required GSP data collection
  - Visit 3 GSP 2, and the required GSP data collection
  - Visit 4 (Day 1) Re-screening/Baseline GSP 3 and HDSM-Ax, and the required GSP and HDSM-Ax data collection
  - Visit 10 (GSP 4) Day 41 ( $\pm$  2 days), and the required GSP data collection
  - Visit 11 (GSP 5) Day 42 ( $\pm$  2 days), and the required GSP data collection
  - Visit 12 (GSP 6) Day 43 (± 2 days) and HDSM-Ax, and the required GSP and HDSM-Ax data collection

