#### Modified Intent-to-Treat (mITT) Population

The mITT Population will be a subset of the ITT Population and excludes subjects with duplicate enrollments either within BBI-4000-CL-302 or across BBI-4000-CL-301 and BBI-4000-CL-302 (see Section 3.3). All other subjects will be analyzed according to the treatment group to which they were randomized, regardless of post-randomization protocol deviations, including no treatment or wrong treatment received.

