#### 5.2 **Protocol Violations**

Major protocol violations will be summarized by treatment group for the Safety Population. Major protocol violations may include, but will not be limited to the following:

- Not meeting eligibility criteria;
- Randomization error;
- Received no protocol treatment or wrong treatment;
- Non-compliance with study drug dosing;
- On-study administration of a prohibited medication;
- Unauthorized changes to protocol procedure that could potentially affect subject safety or are a flagrant deviation of protocol defined procedures.

All major protocol violations will be determined and appropriately categorized prior to database lock and prior to breaking the blind of the treatment group assignments. The number and percentage of subjects with any major protocol violations as well as the number and percentage of subjects with violations within each category will presented. A per subject listing will be provided for all protocol violations, major or minor, for the Safety Population.

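### The Per-Protocol set has no study-drug criterion, so untreated or wrongly treated subjects who complete the listed visits stay in it

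*SAP*

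**What the plan says.** SAP Section 4 opens the definition with "The PP Population will be a subset of the mITT Population and will include subjects who meet the following criteria". Three criteria follow: "Meets all inclusion/exclusion criteria"; "Has not taken or applied any interfering concomitant medications"; and "Completed the following visits", which names Visits 2, 3, 4, 10, 11 and 12 with their GSP data, plus HDSM-Ax data at Visits 4 and 12. Protocol 10.1.2 and the protocol synopsis use the same criteria, with ITT as the parent set.

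The parent set in the SAP is mITT. It removes duplicate enrolments and keeps everyone else in the randomised arm "regardless of post-randomization protocol deviations, including no treatment or wrong treatment received".

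SAP 5.2 deals with protocol violations. It begins "Major protocol violations may include, but will not be limited to the following" and lists, among other items, randomisation error, "Received no protocol treatment or wrong treatment" and "Non-compliance with study drug dosing". These are to be settled before database lock and before the blind is broken. Nothing in 5.2 ties the list to PP membership.

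SAP 8.3.7 calls PP a completers set, analysed on observed data. It applies PP to all secondary and exploratory endpoints and, as an exploratory analysis, to the co-primary endpoints.

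**The concern.** A set labelled Per-Protocol is normally read as the subjects who followed the protocol, including on treatment. Here the most basic part of following it, receiving the assigned product, is not tested. Nor does the parent set supply the test, because mITT keeps untreated and wrongly treated subjects by design.

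What is at stake is interpretation. If PP and ITT results agree, a reader may take this as evidence that treatment errors and omissions did not matter. The PP set cannot show that, because such subjects can be in both sets. A vehicle-arm subject who received active gel would count as active in the Safety Population and as vehicle in PP.

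**Working it through.** The plan states no figure on this point, so the check is mainly of text, followed by a short calculation of size.

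**Step 1. Each SAP 5.2 category against the PP criteria.**

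| SAP 5.2 category | Removed from PP? |
|---|---|
| Eligibility failure | Yes, by the eligibility criterion |
| Prohibited medication on study | Yes in substance, by the interfering-medication criterion |
| Randomisation error | No |
| No treatment or wrong treatment | No |
| Dosing non-compliance | No |
| Unauthorised procedure changes | Only if a listed visit or its data are missing |

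The three categories that concern assignment or use of study drug are the three that no PP criterion reaches.

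**Step 2. Other rules that might close the gap.**
- Inclusion criterion 5 (Protocol 4.2) concerns ability at entry, not what was applied.
- Protocol 7.4 allows discontinuation for non-compliance but does not require it.
- SAP 5.1 reports reasons for exclusion from PP but adds no criterion.
- SAP 4 requires at least one dose for the Safety Population. PP is not required to be a subset of that population.
- SAP 7 derives exposure but does not use it to define PP.
- The visit criterion removes untreated subjects who stop attending. Those who complete all six visits remain.

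None of these removes an untreated or wrongly treated subject who completes the visits.

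**Step 3. Possible size.** SAP 2.6 assumes HDSM-Ax-7 response rates of 53.7% (active) and 29.8% (vehicle):

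53.7 − 29.8 = 23.9 points.

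If a fraction f of active-arm PP subjects responds at the vehicle rate, the PP difference becomes (1 − f) × 23.9, a loss of f × 23.9. The documents give no value for f, so a range is assumed:
- f = 0.02: 0.02 × 23.9 = 0.478, about 0.5 points
- f = 0.05: 0.05 × 23.9 = 1.195, about 1.2 points

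**Step 4. Whether existing measures could support a compliance criterion.** SAP 5.2 gives no cut-off. SAP 7 counts expected doses only from first to last dose. Planned applications are 42 days × 2 axillae = 84. Take a subject who applies every dose for 10 days, stops, and keeps attending:
- by SAP 7: (10 × 2) / (10 × 2) = 20/20 = 100%
- against the plan: 20/84 = 23.8%

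A compliance rule built on the SAP 7 measure would pass this subject.

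**Step 5. Where violations are reported.** SAP 5.2 summarises and lists violations for the Safety Population, which requires at least one dose. A never-treated subject cannot appear there, so the planned outputs would not identify such subjects for PP purposes.

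**The case against.** The strongest reply is that the SAP does not claim more for PP than it delivers. Section 8.3.7 openly calls it a completers set, and no passage calls it an adherence or on-treatment analysis. No decision rests on it: the co-primary estimands are in ITT regardless of adherence, the secondary endpoints are gated in ITT (SAP 8.3.6), and dilution of a superiority comparison runs towards no difference. The situation should also be uncommon. Containers are assigned through IRT and weighed, compliance is asked about at Visits 5 to 12, and a subject who never used the gel would have to attend three end-of-treatment visits.

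Much of this stands. It limits the consequence to labelling and supportive interpretation, and it makes the case less likely. It does not supply the missing criterion or make the Per-Protocol label fit the content.

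A reader might go further and infer that PP should also drop every poorly compliant subject, simply by importing the SAP 5.2 categories with no new threshold. The documents do not support that. The 5.2 list is of what major violations may include, so it does not automatically classify every case. Its compliance item has no cut-off, and Step 4 shows that the SAP 7 measure cannot stand in for one. Compliance is also a post-randomisation outcome that may be related to tolerability and so differ by arm; excluding on it can introduce selection bias even when done blind. It would also be unclear how to treat gel withheld on protocol instruction for suspected allergic contact dermatitis (Protocol 8.1.7, SAP 9.2.1).

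**Conclusion.** The gap is real and minor. As written, PP keeps untreated and wrongly treated subjects, and those with a randomisation error, provided they meet the eligibility and medication criteria and complete the six visits. This affects the PP analyses of the co-primary, secondary and exploratory endpoints. It does not affect the ITT conclusion.

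The number of such subjects is unknown. The loss of 0.5 to 1.2 points out of 23.9 rests on an assumed 2% to 5% of active-arm PP subjects and on their responding exactly like vehicle. Subjects who used some active gel would dilute the difference less. Vehicle subjects given active gel would add to the dilution and are not counted. On dosing compliance, the documents support only a conditional recommendation, because they contain neither a threshold nor a suitable measure.

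**What to change.** Add one PP criterion to SAP 4: *received the randomised study product, with no randomisation error and no wrong treatment, as classified for all randomised subjects before unblinding*. This needs no numerical threshold and fits the existing plan to settle populations and violations before lock. The classification must cover all randomised subjects, not only the Safety Population. Because the protocol's PP definition lacks this criterion, record the change in SAP 13.

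Add a dosing-compliance criterion only if the cut-off is fixed before unblinding, is measured against the 84 planned applications, and comes with a statement of how protocol-directed interruptions count. Otherwise, describe the set as completers in the table titles or footnotes.

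The cost is a short SAP edit, an entry in SAP 13, and a slightly smaller PP set. If compliance is used, possible selection bias from a post-randomisation exclusion is a further cost and should be acknowledged with the results.

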#### Modified Intent-to-Treat (mITT) Population

The mITT Population will be a subset of the ITT Population and excludes subjects with duplicate enrollments either within BBI-4000-CL-302 or across BBI-4000-CL-301 and BBI-4000-CL-302 (see Section 3.3). All other subjects will be analyzed according to the treatment group to which they were randomized, regardless of post-randomization protocol deviations, including no treatment or wrong treatment received.

### 5. STUDY SUBJECTS

#### 5.1 Disposition of Subjects

Subject disposition will be summarized by treatment group for Safety, ITT, mITT, and PP populations separately. Summaries will include the number and percentage of subjects completing treatment, completing the study, and discontinuing the study early by the primary reason for discontinuation. The number and percentage of subjects excluded and reason for exclusion will be included in the PP population disposition table.

All subject disposition data will be listed by clinical site.

#### 5.2 **Protocol Violations**

Major protocol violations will be summarized by treatment group for the Safety Population. Major protocol violations may include, but will not be limited to the following:

- Not meeting eligibility criteria;
- Randomization error;
- Received no protocol treatment or wrong treatment;
- Non-compliance with study drug dosing;
- On-study administration of a prohibited medication;
- Unauthorized changes to protocol procedure that could potentially affect subject safety or are a flagrant deviation of protocol defined procedures.

All major protocol violations will be determined and appropriately categorized prior to database lock and prior to breaking the blind of the treatment group assignments. The number and percentage of subjects with any major protocol violations as well as the number and percentage of subjects with violations within each category will presented. A per subject listing will be provided for all protocol violations, major or minor, for the Safety Population.

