10.1.3 Safety Population

The Safety Population will include all subjects randomized in the study who received study drug, either vehicle or sofpironium bromide gel, 15%, at least once. If a subject received any sofpironium bromide gel, 15%, the subject will be analyzed in the sofpironium bromide gel, 15%, treatment group. Otherwise the subject will be included in the vehicle group.

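### Major protocol violations are tabulated only on the Safety Population, so violations in randomised but never-dosed subjects, including never being treated, cannot be counted

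*SAP*

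**What the plan says.** SAP 5.2 sets the population for the violation summary: "Major protocol violations will be summarized by treatment group for the Safety Population". A later sentence in the same section puts the per-subject listing of all violations, major or minor, on the Safety Population too. The planned outputs agree: Table 14.1.1.2 (SAP 15) and Listing 16.2.2 (SAP 17) are both marked Safety, and no ITT version of either is planned.

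SAP 5.2 gives an open-ended list of what may count as a major violation. One entry is "Received no protocol treatment or wrong treatment". Others include failed eligibility and randomisation errors.

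SAP 4 defines the population: "The Safety Population will include all subjects randomized in the study who received study drug, either vehicle or sofpironium bromide, 15%, at least once". On grouping it adds: "Subjects will be analyzed according to the treatment actually received". Anyone who receives any 15% gel goes into the active group. Protocol 10.1.3 sets the same condition of at least one receipt of study drug.

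The plan foresees randomised subjects who are never treated. The ITT Population keeps subjects in their randomised arm "regardless of post-randomization protocol deviations, including no treatment or wrong treatment received". SAP 3.2 sets a reference day for them: "Note that if the subject is randomized but not treated then the randomization date will be Day 1".

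**The concern.** The plan names a violation and then tabulates it in a population from which everyone who commits it is excluded. A reader of the study report would see no untreated subjects in the table and could take this as evidence of good conduct, when it follows only from the choice of population.

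The situation can arise in practice. Under Protocol 7.2.3 subjects are randomised at Visit 4 and apply the first dose at home that evening, so a subject can be randomised and never dose. If that subject also failed an eligibility criterion or was randomised in error, that violation is lost from the table as well.

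Grouping by treatment received adds a second difficulty. The primary analysis is ITT by randomised arm, whereas for some subjects the violation table would show the wrong-treatment error in the other arm. It would then not show in which randomised arm the error arose.

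**Working it through.** The plan gives no figure to reproduce here. The check is a comparison of definitions.

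**Step 1: the no-treatment count.** Inputs: SAP 4, Protocol 10.1.3 and the SAP 5.2 category list.

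- Safety Population = randomised and dosed at least once.
- Received no protocol treatment = randomised and never dosed.
- No subject can belong to both sets, so the count is zero whatever happens in the trial.

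**Step 2: other violations in the same subjects.** A never-dosed subject contributes to neither the numerator nor the denominator of Table 14.1.1.2, so an eligibility failure or randomisation error in that subject is not counted.

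**Step 3: where wrong-treatment violations fall.** Protocol 5.2 has two pumps dispensed, at Visits 4 and 7, so mixed exposure is possible. Applying the SAP 4 grouping rule:

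- Randomised to vehicle, received any 15% gel: counted under active, not the assigned arm.
- Randomised to active, received only vehicle: counted under vehicle, not the assigned arm.
- Randomised to active, received both products: counted under active, the assigned arm.

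**Step 4: size.** Let u be the number randomised but never dosed. The documents do not give u. With the planned 350 randomised:

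- Present rule: 0 / (350 − u) for every u.
- ITT rule: u / 350.

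For illustration only, take u from 0 to 10. This range is an assumption with no support in the documents.

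- u = 0: 0 / 350 = 0%, and the two rules agree.
- u = 1: 1 / 350 = 0.3% under ITT, against 0 / 349 = 0% now.
- u = 10: 10 / 350 = 2.9% under ITT, against 0 / 340 = 0% now.

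**Step 5: what other planned outputs show.** SAP 5.1 tabulates disposition for ITT as well as Safety (Table 14.1.1.1.2 is the ITT version). Listings 16.2.1 (disposition) and 16.2.3 (analysis populations) cover all randomised subjects. The Per-Protocol disposition table reports exclusions with reasons, and eligibility is a Per-Protocol criterion. Never-dosed subjects can therefore be identified, but none of these outputs tabulates violations by category.

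**The case against.** The strongest reply is that little is lost. Untreated subjects appear in the ITT disposition table and in two all-randomised listings, and an eligibility failure in one of them may appear among the Per-Protocol exclusion reasons. The efficacy analysis keeps them in their randomised arm. This stands, and it limits the point to reporting. It does not supply the missing violation categories.

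A second reply concerns the listing. SAP 3.1 has a general convention that data from subjects outside an analysis population are still shown in listings. That may bring never-dosed subjects back into Listing 16.2.2, although SAP 5.2 and the listing's own population entry restrict it to Safety. The two texts need reconciling. The convention cannot rescue the table, because the same sentence keeps such subjects out of summary statistics.

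A third reply is that the category list is only illustrative and that the entry combines no treatment with wrong treatment. Both statements are correct. A reader might infer that the whole entry is empty by construction, but it is not: wrong treatment can still be counted in dosed subjects. A reader might also infer that every wrong-treatment case changes arm. The SAP 4 rule does not support that, because an active-randomised subject who received both products stays in the assigned arm.

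**Conclusion.** The point holds as a reporting defect of low severity. As written, the no-treatment count in Table 14.1.1.2 is fixed at zero, other violations in never-dosed subjects are omitted, and some wrong-treatment violations are shown under the arm not assigned. For untreated subjects the undercount is exactly the number randomised but never dosed. That number is unknown from the documents and may be zero.

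A reader might infer that the table drops or moves the most serious violations, or that the integrity of the primary comparison is in doubt. The documents support neither. They do not rank violations by seriousness within the major class, and violations in dosed subjects all remain in the table. SAP 5.2 does not assign the table the purpose of validating the ITT comparison. No efficacy or safety estimate changes.

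The conclusion rests only on the population definitions. The percentages above illustrate scale and are not estimates.

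**What to change.** In SAP 5.2, change the population in both sentences (summary and per-subject listing) from Safety to ITT, that is, all randomised subjects, grouped by randomised arm. Make the same change in the population entries for Table 14.1.1.2 and Listing 16.2.2. Keep a Safety version by treatment received as an additional output if it is wanted. This also removes the conflict between the Safety-only listing and the general listing convention in SAP 3.1.

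The cost is two sentences and two population entries, plus the grouping variable in the programs. No new data are needed. SAP 5.2 already requires major violations to be determined and categorised before database lock and unblinding, so only the denominator and the grouping change.
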